3.10.2 Retention

Due to the design and short duration of the trial, no plans for participation retention will be required.

3.11 Data management

Data Forms and Data Entry

In the High flow nasal oxygen (HFNO) during sedation trial, all data will be entered electronically using REDCap. No identifying information will be included in the database. A study ID will be assigned for each study participant and only this will be entered into the REDCap database. A majority of this will occur on site where the data originated at the Peter Munk Cardiac Cath cardiac cath labs, however some instances may occur at the PI's office located in the Peter Munk Cardiac Centre, Toronto General Hospital. Original study forms will be entered and kept on file at the participating hospital site.

All personal information such as the patient's name, date of birth, health information, and UHN MRN will be removed from the data and will be replaced with a participant ID number. A list linking the participant ID number with patient names will be stored in an electronic file by the study team on a secure UHN Network in compliance with UHN's policy and procedural manual on storage, transport and destruction of confidential information.

Data Transmission and Editing

Using REDCap™, range checks will be applied to minimize errors in data entry.

Security and Back-Up of Data

All forms related to study data will be kept in locked cabinets. Access to the study data will be restricted. A password system will be utilized to control access to electronic files related to the study on a secure UHN Network in compliance with UHN's policy and procedural manual on storage, transport and destruction of confidential information. These passwords will be changed on a regular basis. In compliance with UHN's policy & procedure manual on “Research: Data Ownership, Stewardship & Security of Health Information”, the institution will be responsible for providing hard data backs ups of all UHN Information and Technology (IT) systems for disaster recovery purposes.

Data Storage In accordance with the UHN Administrative - Management, Retention & Disposal of Administrative Record policy 1.30.007, the study data will be retained for 10 years.

3.12 Statistical methods

3.12.1 Outcomes

For the primary outcome, peak TcCO₂ will be compared between the intervention and control groups using a Bayesian hierarchical model with baseline TcCO₂ concentration included in the model as a covariate as is recommended for this type of design.²⁶ Bayesian models will also be used to compare secondary outcomes among the randomization groups. Prior distributions for all model parameters will initially be chosen to be non-informative and will be adjusted as necessary to improve model fit. The posterior distributions of parameters and quantities of interest will be presented as well as their medians and 95% highest-density intervals (HDI). Subgroup analyses will be conducted to compare the effects of HFNO with standard care in patients who have a diagnosis of sleep apnea and those who have a cardiac resynchronization therapy device implant (the variables used for stratification) by including these variables in the model as interaction terms.

In addition to comparing the peak TcCO₂, per-second TcCO₂ levels will be compared between randomization groups using methods of functional data analysis. Functional observations will be estimated by fitting a B-spline basis to the TcCO₂ data, subject to a roughness penalty on the second derivative of the estimated function. Common features of these estimated functions will be examined using functional principal component analysis (FPCA). A formal comparison of TcCO₂ levels between randomization groups will be performed using functional analysis of variance (FANOVA). Results of this functional analysis will be compared to those obtained in the bayesian analysis on just the peak TcCO₂ levels.

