3 METHODS

3.1 Study setting

Peter Munk Cardiac Centre Cardiac Cath Labs at Toronto General Hospital, University Health Network.

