3.4 Outcomes

The selection of outcomes was informed by recommendations from the Sedation Consortium on Endpoints and Procedures for Treatment, Education and Research (SCEPTER) to assess differences between groups regarding the safety and efficacy of sedation.

Primary outcome: Peak transcutaneous carbon dioxide (TcCO₂) concentration.

Continuous TcCO₂ measurements will be recorded using the Sentec Digital Monitoring with VSign 2 sensor. TcCO₂ monitoring provides continuous, accurate (mean bias -0.1 mmHg) and precise (95% limits of agreement within 6 mmHg) estimates of arterial CO₂ (PaCO₂) when the sensor is placed on the earlobe.¹⁴ TcCO₂ monitoring may provide even more precise estimates of changes in PaCO₂ (mean bias 0.03 mmHg, 95% limits of agreement -0.44 to 0.38 mmHg).¹⁵

We have undertaken a preliminary study to evaluate the feasibility of using TcCO₂ monitoring as an outcome measure during nurse-administered sedation in the cardiac catheterisation laboratory. Continuous TcCO₂ measurements were recorded from patients undergoing procedures with nurse-administered sedation using the Sentec Digital Monitoring with VSign 2 sensor, starting before sedation was induced (for measurement of baseline TcCO₂) and ceasing at the end of the procedure. Participating sites were the Wesley Hospital, Holy Spirit Northside Private Hospital, Princess Alexandra Hospital and John Flynn Private Hospital. The feasibility of TcCO₂ monitoring in this population was confirmed with continuous recordings achieved from all participants without missing data. Changes in TcCO₂ concentrations are presented in Table 1.

Table 1. Changes in TcCO₂ concentrations during sedation (n=123)

	Mean	SD
Baseline pre-sedation TcCO ₂	37.3	4.6
Post-sedation mean TcCO ₂	42.3	5.8
Peak TcCO ₂	46.8	6.9
Change from baseline to peak TcCO ₂	9.4	5.6

Secondary outcomes

1. Mean transcutaneous carbon dioxide concentration measured throughout the whole procedure using the VSign 2 sensor.
2. Trajectory of transcutaneous carbon dioxide concentration as a function of time throughout the whole procedure using the VSign 2 sensor.
3. Area under the curve of oxygen desaturation: This is a composite measure comprising the incidence, depth, and duration of oxygen desaturation events. It is calculated as the difference between the threshold (90%) and actual oxygen saturation (SpO₂) summed every second during which oxygen saturation was below threshold).

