3.6 Sample size

We estimate based on data from our preliminary study that the peak TcCO₂ level in the control group will be 47 mmHg and standard deviation in both groups will be 7 mmHg. Assuming a type I error rate of 5%, a sample of 130 participants would achieve 90% power to detect a reduction in mean TcCO₂ levels of 4 mmHg in the intervention period. A difference in TcCO₂ levels of 4 mmHg was selected for this sample size calculation because it was used to power previous randomized controlled trials of the effect of oxygen supplementation on ventilation status in other populations, with the authors noting that an effect of this magnitude was of physiological significance.^{16,17} Also, differences in CO₂ levels of a similar magnitude have been detected in previous trials evaluating the efficacy of interventions to improve sedation safety.¹⁸⁻²² To account for any missing primary outcome data (in the event that the TcCO₂ monitor malfunctions) and dropouts (in the event that a randomized patient's procedure is cancelled or anesthetic management plan is changed prior to procedure commencement), we plan to recruit a sample of 150 participants.

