3.8 Allocation

Consented eligible patients will be allocated randomly to intervention and control groups. A stratified (by diagnosis of obstructive sleep apnea and type of procedure – cardiac resynchronization therapy device implant), block randomized sequence will be generated using the redcapAPI package in R and uploaded to REDCap™. The RA will retrieve the allocation for each consecutive participant in REDCap™ prior to the procedure.

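### Randomization is stratified by sleep apnea and CRT implant, but the primary peak TcCO₂ model names only baseline TcCO₂; adding the strata is free and may slightly narrow the interval

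*Combined protocol and SAP*

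**What the plan says.** Section 3.8 (Allocation) describes the sequence as "A stratified (by diagnosis of obstructive sleep apnea and type of procedure", the procedure type being CRT device implant. That is two binary factors and four cells, in blocks of unstated size.

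Section 3.12.1 (Outcomes) compares peak TcCO₂ between arms "using a Bayesian hierarchical model with baseline TcCO₂ concentration included in the model as a covariate". Later in the same paragraph, the subgroup analyses for sleep apnea and CRT implant are to be done "by including these variables in the model as interaction terms". On reporting, it says "The posterior distributions of parameters and quantities of interest will be presented", without naming which treatment quantity is the primary one.

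Section 3.1 gives a single site, "Cardiac Cath Labs at Toronto General Hospital", and the primary outcome is one peak value per patient. No section says what the levels of the hierarchical model are.

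Section 3.6 (Sample size) states that "a sample of 130 participants would achieve 90% power to detect a reduction in mean TcCO₂ levels of 4 mmHg", with an SD of 7 mmHg in both groups.

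**The concern.** Stratified randomization balances the arms on the stratifying factors. If those factors predict the outcome, the balance removes their contribution from the treatment contrast, and the estimate varies less from trial to trial. A model that omits the factors leaves that variation in its residual term, so its standard error and interval do not reflect the gain. The estimate is unbiased, but the interval is conservative.

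The text allows three readings: the strata are absent from the primary model; they are the unstated level of the hierarchy; or they enter the primary model through the interactions. Under the third reading the text does not say that the primary result is the treatment effect averaged over the strata, and not the coefficient for the reference cell.

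What is at stake is a little interval width and a covariate set fixed in advance. Bias and inflated type I error are not at issue.

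**Working it through.** **Plan's own figure.** Two-sided 5%, 90% power, difference 4, SD 7: n per arm = 2 × (1.960 + 1.282)² × 7² / 4² = 64.4, rounded up to 65, so 130 in total. This reproduces Section 3.6, which is an unadjusted comparison.

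**Effect of baseline adjustment.** Table 1 in Section 3.4 gives SDs of 4.6 (baseline), 6.9 (peak) and 5.6 (change). Hence

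r = (4.6² + 6.9² − 5.6²) / (2 × 4.6 × 6.9) = 37.41 / 63.48 = 0.589.

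Residual SD = 7 × √(1 − 0.589²) = 5.66. With 65 per arm, SE = 5.66 × √(2/65) = 0.99 and the 95% interval is about 3.93 mmHg wide. Power for 4 mmHg is about 97.9%.

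**Adding the strata.** Simulated trials: N = 130, stratified permuted blocks of 4, an equal shift per factor, and the strata's variance taken out of the 5.66. Least squares stands in for the Bayesian model with flat priors. Widths and type I error come from 6,000 null trials per row (simulation error about 0.3 points). Not in the documents, and therefore assumed: prevalence 20% sleep apnea and 30% CRT, block size, and the share of residual variance explained.

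| Share explained | Shift per factor (mmHg) | SE, baseline only | SE, strata added | Extra width without strata | Type I error without / with |
|---|---|---|---|---|---|
| 0% | 0 | 0.993 | 0.993 | 0% | 5.1% / 5.1% |
| 2% | 1.3 | 0.994 | 0.985 | 1.0% | 5.1% / 5.3% |
| 5% | 2.1 | 0.995 | 0.971 | 2.5–2.6% (3.94 vs 3.84 mmHg) | 4.5% / 5.0% |
| 10% | 2.9 | 0.994 | 0.943 | 5.4% (3.93 vs 3.73 mmHg) | 4.2% / 5.2% |

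Simulated power for 4 mmHg (4,000 trials per row), without and with the strata: 97.5% and 97.6% at 0%, 97.8% and 98.0% at 5%, 98.5% and 99.0% at 10%.

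**What the change affects.** A separate simulation (25% and 30% prevalence, 8,000 runs) at 10% explained gave an empirical SD of the estimate of 0.948 without the strata and 0.945 with them. Coverage was 96.0% and 95.0%. Stratifying has already delivered the precision; adding the strata mainly makes the interval report it.

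**Form of the strata.** Main effects and a random intercept over the four cells give the same widths: 3.93 and 3.92 mmHg at 0%, 3.84 for both at 5%, 3.73 for both at 10%. If interactions are kept, the effect averaged over the observed strata has SE 0.993, 0.970 and 0.944 at 0%, 5% and 10%, which matches main effects.

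**Sensitivity.** With the share explained held fixed, the extra width is close to 1/√(1 − share) − 1 (2.6% at 5%, 5.4% at 10%) whatever the correlation, prevalence or block size. A more informative check holds the shift at 2.1 mmHg per factor, where share = 2.1² × [p₁(1 − p₁) + p₂(1 − p₂)] / residual variance:

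- Prevalence 10% and 20%, r = 0.589: 4.41 × 0.25 / 31.98 = 3.4%, so 1.8% wider.
- Prevalence 30% and 40%, r = 0.589: 4.41 × 0.45 / 31.98 = 6.2%, so 3.3% wider.
- Prevalence 20% and 30%, r = 0.30 (residual variance 49 × 0.91 = 44.59): 4.41 × 0.37 / 44.59 = 3.7%, so 1.9% wider.
- Prevalence 20% and 30%, r = 0.75 (residual variance 49 × 0.4375 = 21.44): 4.41 × 0.37 / 21.44 = 7.6%, so 4.0% wider.

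**The case against.** The strongest reply is that the plan may already include the strata. Section 3.12.1 puts them into the model as interactions, an interaction normally carries its main effects, and in a single-site trial with one value per patient the strata are an obvious candidate for the hierarchy. The section never says that baseline is the only covariate. This stands as a possible reading, but the text does not settle it, and the interactions are introduced for the subgroup analyses. If it is what the authors meant, one clause saying so closes the point.

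The second reply is that the gain is small and unproven: at most a few per cent of interval width, resting on a prognostic strength that the documents do not give. That stands too. The 10% row needs a 2.9 mmHg shift per factor after baseline adjustment, about 73% of the 4 mmHg target effect, and nothing in the plan supports a shift that large.

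Third, Section 3.12.1 gives no decision rule, so type I error and power here describe a least-squares stand-in, with the 95% interval excluding zero as the criterion. They are not properties of the stated Bayesian analysis. This is a fair limit on those figures. The width comparison depends on it less, provided the priors stay vague.

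**Conclusion.** The concern holds as a minor, optional improvement. No section places the stratification factors in the primary comparison, although the trial randomizes by them. If they are left out, the estimate is unbiased, type I error is not inflated and power for 4 mmHg stays near 98%. The reported interval is too wide by 0% to 5.4% as the share of residual variance explained runs from 0% to 10%. At a fixed 2.1 mmHg shift per factor, it is too wide by about 1.8% to 4.0% across the prevalences and correlations tried. No conclusion of the trial is shown to depend on this.

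The size rests on assumed prevalence, block size and prognostic strength, and on a correlation from Table 1. Those pilot data assessed TcCO₂ monitoring "as an outcome measure during nurse-administered sedation in the cardiac catheterisation laboratory" at other hospitals, whereas here Anesthesia Assistants give the sedation.

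**What to change.** In Section 3.12.1, state that the primary model for peak TcCO₂ includes treatment, baseline TcCO₂, obstructive sleep apnea (yes/no) and CRT implant (yes/no). Say whether the two factors enter as main effects or form the grouping level that hierarchical refers to; either serves. Add that treatment-by-factor interactions are fitted only in the subgroup model or, if they stay in the primary model, that the primary result is the treatment effect averaged over the strata.

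The cost is two or three sentences. Both variables are already recorded for randomization, and no extra patients or data are needed. If the strata turn out not to be prognostic, the SE is 0.993 with or without them. The change covers peak TcCO₂ only; the functional analysis and the other outcomes were not examined here.

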The Optiflow device (Fisher and Paykel Healthcare, Auckland, New Zealand), heated breathing tube and chamber, and nasal cannula will be used. This system is a humidifier with an integrated flow generator, able to humidify respiratory gases and deliver them down a heated breathing tube and through the nasal cannula interface. The gas temperature will commence at the ‘High’ setting (ranges 30-32° Celsius) and titrated downwards if the patient complains of irritation. The gas flow rate will commence at 30 liters per minute prior to sedation administration and be titrated up to 70 liters per minute as tolerated by the patient after sedation has been administered. The fraction of oxygen in the gas will be commenced at 50% (same as that delivered from 6 liters per minute via facemask) and can be titrated upward according to patient requirements (i.e. increased if there is evidence of hypoventilation, airway obstruction or inadequate oxygenation, decreased during use of diathermy). Anesthesia Assistants at the site will be provided with training in the use of this mode of oxygen delivery prior to study commencement.

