3.10 Data collection

3.10.1 Trial procedures and evaluations

Instruments used to measure outcomes

Transcutaneous carbon dioxide concentrations: PI [name] will provide training to the RA in use of the transcutaneous carbon dioxide monitoring device and other data collection procedures. The RA will attach the Sentec VSign 2 sensor to the participant's forehead using a multi-site attachment ring. Once the Sentec Digital Monitoring System displays a stabilized TcCO₂ level, the monitor will be covered with a drape so that it is not visible to research staff or clinicians during the procedure. The monitor will not be used by the clinicians to guide treatment. Data will be downloaded to a computer using the USB port on the monitor. TcCO₂ monitoring provides continuous, accurate (mean bias within 2 mmHg) and precise (95% limits of agreement within 6 mmHg) estimates of arterial CO₂ (PaCO₂) in sedated patients.¹⁴

Pulse oximetry: Percentage of hemoglobin saturated with oxygen (SpO₂) will be measured continuously throughout procedures as part of routine clinical practice through the anaesthetic machine. We will access the DREAM (Drug Reconciliation and Electronic Anesthesia Monitoring) system to download this data. Unreliable SpO₂ measurements will be filtered out if a pulse rate is not detectable.

Tracking and reporting outcomes of procedural sedation tool.²³ This tool was developed, using a consensus process, by members of a multidisciplinary society who had demonstrated capacity, dedication and competence in research and/or clinical experience in procedural sedation. Completion of the tool requires identification and description

of the adverse event, the intervention, the outcome and the overall severity of the adverse event. The Anaesthesia Assistant will be asked to complete this tool at the end of procedures. It takes approximately 2 minutes to complete.

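### The trajectory and mean TcCO₂ comparisons name no baseline covariate, unlike the peak model; adding one should gain precision, provided baseline is read before the oxygen device starts

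*Combined protocol and SAP*

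**What the plan says.** **Adjustment.** Section 3.12.1 compares peak TcCO₂ in a Bayesian hierarchical model "with baseline TcCO₂ concentration included in the model as a covariate as is recommended for this type of design". It then says that the secondary outcomes will also be compared with Bayesian models, and names no covariate for them. Mean TcCO₂ is secondary outcome 1.

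Secondary outcome 2 in section 3.4 is "Trajectory of transcutaneous carbon dioxide concentration as a function of time throughout the whole procedure using the VSign 2 sensor". Its analysis fits penalised B-splines to the per-second record and examines functional principal components. The between-group step is: "A formal comparison of TcCO₂ levels between randomization groups will be performed using functional analysis of variance (FANOVA"). No baseline term is mentioned. The paragraph closes: "Results of this functional analysis will be compared to those obtained in the bayesian analysis on just the peak TcCO₂ levels".

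The only other covariates in section 3.12.1 are the two stratification factors, which serve the subgroup analyses "by including these variables in the model as interaction terms". Section 3.12.2 plans nothing further, so no adjusted version of the trajectory or mean analysis appears elsewhere.

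**Timing of baseline.** For high flow nasal oxygen (HFNO), section 3.3.1 says: "The gas flow rate will commence at 30 liters per minute prior to sedation administration". Section 3.10.1 says: "Once the Sentec Digital Monitoring System displays a stabilized TcCO₂ level, the monitor will be covered with a drape". It does not say whether the allocated device is already running by then. The schedule in section 3.5 puts allocation at T1, puts both oxygen devices and the TcCO₂ measurements at T2, and has no row for baseline TcCO₂. Section 3.4 calls baseline pre-sedation, but only when describing the preliminary study.

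**The concern.** The protocol's reason for adjusting peak TcCO₂ applies equally to a curve, or an average, taken from the same sensor in the same patients. People differ in resting TcCO₂. If that difference carries into the procedure, an unadjusted comparison counts it as noise, so the FANOVA is less sensitive and the interval for mean TcCO₂ is wider than it need be. The plan also sets the functional result beside the peak result. The two already differ in estimand and framework, and unequal adjustment adds one more, avoidable, difference.

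A second issue comes with the remedy. Adjusting for baseline is safe only if the treatment cannot have changed it. HFNO starts before sedation, so a reading that is merely pre-sedation could already have been taken on the device. The primary model uses the same baseline value, so this question reaches the primary outcome as well.

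**Working it through.** **Inputs.** From Table 1 in section 3.4, "Changes in TcCO₂ concentrations during sedation (n=123"): SD of baseline 4.6, of post-sedation mean 5.8, of peak 6.9, and of change from baseline to peak 5.6 mmHg. From section 3.6: SD 7, difference 4 mmHg, type I error 5%, power 90%, 130 participants. Allocation is 1:1 (section 2.3).

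**1. The plan's own figure.** n per arm = 2 × (1.960 + 1.282)² × 7² / 4² = 64.4, rounded up to 65, so 130 in total (two-sided). The stated figure reproduces. It uses the unadjusted SD of peak TcCO₂, so nothing below changes it.

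**2. Baseline–peak correlation.** r = (4.6² + 6.9² − 5.6²) / (2 × 4.6 × 6.9) = 37.41 / 63.48 = 0.589, and r² = 0.347. Rounding of the SDs (±0.05 each) allows 0.573 to 0.605. The Fisher z 95% interval at n = 123 is 0.460 to 0.694.

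**3. What adjustment is worth for peak, which is already adjusted.** SE ratio, unadjusted to adjusted: 1/√(1 − 0.347) = 1.24 (1.22 to 1.26 with rounding; 1.13 to 1.39 with sampling error). At 65 per arm the unadjusted SE is 7 × √(2/65) = 1.23 mmHg. The adjusted SE is 1.23 × √(1 − 0.347) = 0.99 mmHg.

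**4. The curve and the mean, where r is an assumption.** Table 1 gives no SD of change for the post-sedation mean or for any time point, so r cannot be derived. The SE ratio 1/√(1 − r²) does not depend on the SD. For scale, the SEs below use SD 5.8 and 65 per arm.

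| Assumed r | SE without baseline | SE with baseline | Ratio |
|---|---|---|---|
| 0.3 | 1.02 | 0.97 | 1.05 |
| 0.59 (value for peak) | 1.02 | 0.82 | 1.24 |
| 0.8 | 1.02 | 0.61 | 1.67 |

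The correlation may fall late in the procedure, and the gain would fall with it.

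**5. Cost of the extra term.** At 130 patients it adds about 1/126 = 0.8% to the variance at any time point. Adjustment breaks even at r² of about 0.008, that is r of about 0.09.

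**6. Validity either way.** A permutation FANOVA was simulated with 65 per arm, SD 5.8, an assumed smooth within-patient correlation, an assumed constant r, and 400 runs per setting. Type I error was 0.05 to 0.06 with and without baseline. For an illustrative constant difference of 2.5 mmHg, power without and with baseline was 0.86 and 0.93 at r = 0.4, 0.82 and 0.98 at r = 0.59, and 0.77 and 1.00 at r = 0.75.

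**7. Timing of baseline.** Slope of peak on baseline = 37.41 / (2 × 4.6²) = 37.41 / 42.32 = 0.884 (0.847 to 0.923 with rounding). The adjusted difference is the raw difference minus slope × baseline difference. If HFNO had already lowered baseline by 1 mmHg, a raw peak difference of −4 would become −4 + 0.884 = −3.1 mmHg.

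**The case against.** The strongest reply is that nothing here is an error. The FANOVA as written is valid, the outcome is secondary and did not size the trial, and the plan is silent on a baseline term without excluding one. That stands, and it is why this is an improvement to make and not a defect that undermines the trial.

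A reader might take 24% as the loss in the FANOVA. The documents do not support that. The figure is derived for peak, which is already adjusted, and from nurse-administered sedation at other hospitals. For the curve the size is unknown within the assumed 5% to 67%.

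It can also be said that the gain is not free, because adjusting for a baseline read on HFNO would give away part of the effect. This is correct as a condition, and meeting it needs a data-collection instruction as well as analysis wording. But the peak model already carries the same exposure, so the instruction is needed whether or not the FANOVA changes.

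A reader might go further and infer that baseline will be read on the device, or that the primary result is biased. The documents show only that the order is not stated.

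**Conclusion.** The point holds as a recommended, low-cost gain in precision for two secondary outcomes, trajectory and mean TcCO₂. The plan adjusts peak for baseline and names no baseline term for the other two, and no other section supplies one. The gain runs from small (SE 5% larger without baseline at an assumed r = 0.3) to large (67% at r = 0.8). The peak value of 0.59 lies between these but is not evidence about the curve. No bias arises from omitting baseline, and no detectable difference is claimed for the FANOVA.

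The missing baseline term does not touch the primary analysis. The undefined timing of the baseline reading does: about 0.9 mmHg of the adjusted peak difference is lost for each 1 mmHg by which the device had already lowered baseline, if the Table 1 slope carries over to this trial. Whether any such shift would occur cannot be told from the documents. The sample size is unaffected.

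**What to change.** - In section 3.12.1, specify the trajectory comparison as function-on-scalar regression (functional ANCOVA) with treatment and baseline TcCO₂, letting the baseline coefficient vary over time.
- In the same section, include that baseline value as a covariate in the Bayesian model for mean TcCO₂.
- In sections 3.10.1 and 3.12.1, define baseline TcCO₂ as the stabilized reading taken before the allocated oxygen device is started, and use this one value in the peak, mean and trajectory models.

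The cost is a few sentences, one ordering instruction for the Research Assistant, and one extra coefficient function at about 130 patients. No participants or visits are added, and the primary model already needs a baseline reading. The changes should be made before outcome data are seen, so that the choice between adjusted and unadjusted curves cannot depend on the results.
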